8.2. Schedule of Visits and Assessments

The schedule of visits and assessments is shown in [Table 3](#).

A visit window of ± 2 days is allowed throughout the treatment period and during the follow-up period. For a missed visit, the site must contact the subject to reschedule.

Premature discontinuation procedures are provided in [Section 7.3](#). Subjects who discontinue study drug but are willing to come in for further assessments will be asked to complete the ET visit (same assessments as Visit 27, [Table 3](#)) followed by 2 safety follow-up visits 2 and 4 weeks after the ET visit (same assessments as Visits 28 and 29 in [Table 3](#)). They will then be asked to return to the study center for monthly visits according to the schedule outlined in [Table 3](#), to collect the following information: weight assessments, any new antipsychotic medications the subject is taking, and adverse events.

Table 3: Schedule of Visits and Assessments

Visit ^a	Treatment Period																										Follow-Up Period			
	1 ^b	2	3	4	5	6	7	8	9	10	11	12	13	14	15	16	17	18	19	20	21	22	23	24	25	26	27/ ET	28 ^c	29	
Study week	-	2	4	6	8	10	12	14	16	18	20	22	24	26	28	30	32	34	36	38	40	42	44	46	48	50	52	54	56	
Informed Consent	X																													
Eligibility Criteria	X																													
Pregnancy Testing ^d	X						X					X							X											
Urine Drug Screen ^e	X						X					X							X								X			
Weight ^f		X	X	X	X		X		X		X		X		X		X		X		X		X		X		X		X	
Waist Circumference		X	X	X	X		X		X		X		X		X		X		X		X		X		X		X		X	
Vital Signs ^g		X	X	X	X		X		X		X		X		X		X		X		X		X		X		X		X	
Laboratory Samples ^h			X				X					X							X								X			
ECG			X				X					X							X								X			
Physical Exam			X				X					X							X								X			
PANSS ⁱ		X	X		X		X					X							X								X			
CGI-S		X	X		X		X		X		X		X		X		X		X		X		X		X		X		X	
AE ^j		X	X	X	X	X	X	X	X	X	X	X	X	X	X	X	X	X	X	X	X	X	X	X	X	X	X	X	X	X
ConMed Review ^j		X	X	X	X	X	X	X	X	X	X	X	X	X	X	X	X	X	X	X	X	X	X	X	X	X	X	X	X	X
C-SSRS ^k		X	X	X	X	X	X	X	X	X	X	X	X	X	X	X	X	X	X	X	X	X	X	X	X	X	X	X	X	X

Table 3: Schedule of Visits and Assessments (Continued)

Visit ^a	Treatment Period																											Follow-Up Period	
	1 ^b	2	3	4	5	6	7	8	9	10	11	12	13	14	15	16	17	18	19	20	21	22	23	24	25	26	27/ET	28 ^c	29
Study week	-	2	4	6	8	10	12	14	16	18	20	22	24	26	28	30	32	34	36	38	40	42	44	46	48	50	52	54	56
Abnormal Movement Scales ^l			X				X						X						X								X		
IWQOL			X				X						X						X								X		
EQ-5D			X				X						X						X								X		
Cigarette Use			X				X						X						X								X		
Emergency Treatment Card ^m	X	X	X	X	X	X	X	X	X	X	X	X	X	X	X	X	X	X	X	X	X	X	X	X	X	X	X	X	X
Study Drug Dispensation	X	X	X	X	X	X	X	X	X	X	X	X	X	X	X	X	X	X	X	X	X	X	X	X	X	X	X	X	X
Study Drug Adherence Review		X	X	X	X	X	X	X	X	X	X	X	X	X	X	X	X	X	X	X	X	X	X	X	X	X	X	X	X

Abbreviations: AE=adverse event; CGI-S=Clinical Global Impression-Severity; ConMed=concomitant medications; C-SSRS=Columbia-Suicide Severity Rating Scale; EOT=end of treatment; ECG=electrocardiogram; EQ-5D=EuroQol five dimensions questionnaire; IWQOL=impact of weight on quality of life; PANSS=Positive and negative syndrome scale

^a A visit window of ±2 days is allowed throughout the treatment period and during the follow-up period.

^b Visit 1 must occur within 7 days of the end of treatment visit (Visit 17) of the antecedent study, ALK3831-A303, and may occur on the same day. Assessments from ALK3831-A303 Visit 17 will constitute the baseline/screening assessments for this extension study.

^c Follow-up visits (Visits 28 and 29) are not required for subjects who enroll in ALK3831-A308

^d Urine pregnancy test at Visit 1 and at all subsequent specified visits.

^e Urine drug screen via dipstick prior to study drug dispensation at Visit 1, Visit 7, Visit 13, Visit 19 and Visit 27. Urine drug screen tests include, tests for opiates (including codeine, hydrocodone, hydromorphone, methadone, morphine, oxycodone, and oxymorphone) and drugs of abuse (including amphetamine/methamphetamine, phencyclidine [PCP], and cocaine)

^f Subjects that prematurely discontinue study drug will be asked to come in for monthly follow-up assessments of weight, adverse events and any new antipsychotic medications following an early termination (ET) visit and two safety follow-up visits.

-
- ^g Vital signs include orthostatic blood pressure and heart rate, respiratory rate, and oral body temperature. Orthostatic blood pressure and pulse rate will be taken after the subject has been supine for 5 minutes and once again after the subject has stood for 2 minutes.
- ^h Subjects must fast (no food or drink except water) for at least 8 hours before lab draws. Lab draws are to be conducted in the morning for all specified visits.
- ⁱ PANSS should be administered before other psychiatric assessments at each specified study visit.
- ^j Adverse events ongoing at the end of trial or concomitant medications continuing from the antecedent study will be carried over and followed through until resolution
- ^k The “Since Last Visit” version to be used at all visits.
- ^l Abnormal movement scales include the following: Abnormal Involuntary Movement Scale (AIMS), Barnes Akathisia Rating Scale (BARS), and Simpson-Angus Scale (SAS).
- ^m Emergency treatment card to be dispensed at Visit 1, confirmed at subsequent timepoints, and collected at Visit 27, EOT.

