7.3. Subject Withdrawal

A subject may be discontinued from the study at any time if the subject, investigator, or the sponsor determines that it is not in the best interest of the subject to continue participation. If a subject has an absolute neutrophil count (ANC) $< 1.0 \times 10^3$ per μL or glycosylated hemoglobin (HbA1c) $\geq 6.5\%$ at any time during this extension study, the subject will be discontinued from the study. Other reasons for discontinuation include the following:

- Adverse Event (AE)
- Lack of Efficacy
- Lost to follow-up
- Withdrawal by subject
- Protocol Deviation (non-compliance with study drug or study procedures)
- Pregnancy
- Study terminated by sponsor
- Other

If a subject withdraws from the study for any reason, he or she will be asked to return to the clinic for an early termination (ET) visit. The ET visit should be scheduled as close as possible to the subject's last dose and will mimic the assessments scheduled to be conducted at the end of treatment (EOT) visit (Visit 27, [Table 3](#)). Following the ET visit, subjects who discontinue study drug but are willing to come in for further assessments will be asked to complete 2 safety follow-up visits 2 and 4 weeks after the ET visit (same assessments as Visits 28 and 29 in [Table 3](#)). They will then be asked to return to the study center for monthly visits according to the schedule outlined in [Table 3](#) for follow-up weight assessments, adverse events, and documentation of any new antipsychotic medications the subject is taking.

Following ET, any ongoing AEs will be followed until resolution, or until deemed stable by the investigator, or until the subject is deemed by the investigator to be lost to follow-up. If, in the opinion of the investigator, it is necessary to monitor a subject beyond the safety follow-up visit, the follow-up period may be extended as necessary. In such instances, the sponsor and the investigator will agree to an acceptable follow-up schedule.

In the event that a subject chooses to withdraw from the study, the investigator should make a reasonable effort to ascertain the reason(s) for withdrawal, while fully respecting the subject's rights. If the subject fails or refuses to return to the study center, an attempt must be made to contact the subject by telephone in order to assess as many safety and efficacy parameters as possible. All data collected over the telephone must be documented and kept in the subject's record.

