8. STUDY DESIGN

8.1. Overall Study Design and Plan

Subjects that have completed the 24-week treatment period of the antecedent study [ALK3831-A303](#) within the past 7 days are eligible to be enrolled in the study.

Subjects enrolled in the study will be started on the same olanzapine dose that they had maintained at the end of [ALK3831-A303](#). Subjects taking 20 mg olanzapine (either as OLZ 20 or ALKS 3831 20/10 [20 mg olanzapine/10 mg samidorphan]) will start on ALKS 3831 20/10 in this study and subjects taking 10 mg olanzapine (either as OLZ 10 or ALKS 3831 10/10 [10 mg olanzapine/10 mg samidorphan]) will start on ALKS 3831 10/10 in this study. An intermediate dose, ALKS 3831 15/10 (15 mg olanzapine/10 mg samidorphan), will also be available, and subjects may be titrated to this dose any time after the start of the study at the investigator's discretion. Dosing is flexible throughout the study; however, frequent adjustments are discouraged. Dose adjustments can only be performed on-site at the study center. Subjects requiring dose adjustments between scheduled visits should arrange an unscheduled visit for the following procedures: study drug return, adherence review, AE monitoring and study drug dispensation.

Safety assessments will include AE monitoring, clinical laboratory testing, vital signs, weight/BMI and waist circumference assessments, 12-lead electrocardiograms (ECGs), movement disorder assessments including the Abnormal Involuntary Movement Scale (AIMS), Barnes Akathisia Rating Scale (BARS), and Simpson Angus Scale (SAS), and the Columbia-Suicide Severity Rating Scale (C-SSRS).

Efficacy assessments to evaluate the durability of treatment effect will include Positive and Negative Syndrome Scale (PANSS) and Clinical Global Impressions- Severity (CGI-S).

Additional assessments include Impact of Weight on Quality of Life – Lite Questionnaire (IWQOL-Lite), Cigarette Use, and EuroQol five dimensions questionnaire (EQ-5D).

[figure not shown]
Subjects completing 52 weeks of treatment with study drug will be eligible to continue in the open-label, long-term safety study (ALK3831-A308) and will continue to receive ALKS 3831. Subjects not continuing in the ALK3831-A308 long-term safety study will enter a 4-week safety follow-up period.

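### Table 3 shows no urine pregnancy test at Visit 27/ET or in follow-up, so women who stop early, or complete without entering A308, have no scheduled test at the end of exposure

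*Protocol*

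**What the plan says.** The timing of pregnancy tests rests on one row of protocol Table 3 (Section 8.2), labelled "Pregnancy Testing". Its footnote d requires a "Urine pregnancy test at Visit 1 and at all subsequent specified visits" and does not list those visits. Section 8.3.10.3 also refers to Table 3 for timing.

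In the text version of the table the row has four marks: Visit 1, Visit 7 (Week 12), a third mark read here as Visit 13 (Week 24), and Visit 19 (Week 36). The cells at Visits 27/ET, 28 and 29 are empty. The urine drug screen has the same layout, but its footnote e names the visits: "Visit 1, Visit 7, Visit 13, Visit 19 and Visit 27".

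Under Section 7.3 the early termination visit "will mimic the assessments scheduled to be conducted at the end of treatment (EOT) visit". On timing, the same section says "The ET visit should be scheduled as close as possible" to the last dose, so this visit marks the end of exposure. Willing early stoppers then have the ET visit "followed by 2 safety follow-up visits 2 and 4 weeks after the ET visit", with the content of Visits 28 and 29. After that, by footnote f, they "will be asked to come in for monthly follow-up assessments of weight, adverse events and any new antipsychotic medications".

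Completers who enter A308 "will continue to receive ALKS 3831" and are outside this point. Completers who do not enter A308 have Visits 28 and 29.

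**The concern.** The protocol treats pregnancy on study drug as a serious matter. It requires contraception of everyone not exempt, stops the drug at once if a subject becomes pregnant, asks for a report within 24 hours, and follows the pregnancy to its outcome (Sections 8.4.1 and 13.5). The reporting duty starts when the site becomes aware of the pregnancy. With no scheduled test at exit, awareness depends on the woman recognising and mentioning the pregnancy, or on someone choosing to do an unscheduled test. The later contacts do not look for it either: the monthly visits cover weight, AEs and new antipsychotics, and Section 13.1 says that pregnancy is not an AE.

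The study's only stated objective is long-term safety and tolerability. What is at stake is the woman's own safety and the completeness of the record of exposed pregnancies. No efficacy or safety estimate planned in the SAP is affected.

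**Working it through.** **Is the blank cell real or a reading fault?** The plan states no figure to reproduce, so the first step is to compare rows. Study week = 2 × (visit number − 1).

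| Row in Table 3 | Marks in the text version | Visits named in words |
|---|---|---|
| Pregnancy testing | 1, 7, 12, 19 | none listed (footnote d) |
| Urine drug screen | 1, 7, 12, 19, 27 | 1, 7, 13, 19, 27 (footnote e) |

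Both rows have the same number of cells (31 with the label), and their first four marks sit in the same positions. Footnote e confirms four of the five drug-screen positions, including Visit 27. Only the Week 24 mark is displaced, by one column. The pregnancy row is therefore not cut short: its Visit 27 cell is present and empty.

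Nine other rows are also marked at Weeks 12, about 24, and 36: drug screen, laboratory samples, ECG, physical examination, PANSS, movement scales, IWQOL, EQ-5D and cigarette use. All nine are marked at Visit 27/ET. Pregnancy testing alone is not.

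**Does any other text supply the test?** Footnote d and Section 8.3.10.3 refer back to the table. The ET visit copies Visit 27, and the two visits after it copy Visits 28 and 29. Table 4 lists no pregnancy test. Section 8.4.1 deals with contraception and known pregnancies and schedules no test. The SAP is silent.

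**How old can the last scheduled test be?** Inputs are tests at Weeks 0, 12, 24 and 36; end of treatment at Week 52; last follow-up at Week 56; and a window of ±2 days per visit (Section 8.2). The windowed figures take the test 2 days early and the exit visit 2 days late. For a woman stopping before Week 36, this assumes she exits just as her next test falls due.

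- Exit before Week 36: 12 weeks = 12 × 7 = 84 days; with windows, 84 + 2 + 2 = 88 days.
- Exit from Week 36 to Week 52: 52 − 36 = 16 weeks = 112 days; with windows, 112 + 2 + 2 = 116 days.
- Second safety follow-up visit, 4 weeks after exit: 12 + 4 = 16 weeks for the first group, and 56 − 36 = 20 weeks for the second.

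**With a test at Visit 27/ET:** tests fall at Weeks 0, 12, 24, 36 and 52, with intervals of 12, 12, 12 and 16 weeks. The age of the last test at exit becomes 0 for every woman who attends.

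**The case against.** The strongest objection is that the evidence is one empty cell in a table that the text version reproduces imperfectly. Week 24 marks are displaced in several rows, and the AE row runs one column past the last visit. Study drug dispensation is marked through Visit 29 although Section 9.1 stops it at the end of treatment. The emergency card row also runs through Visit 29 although footnote m collects the card at Visit 27. Footnote d, unlike footnote e, gives no list to check against. This stands in part: a lost mark cannot be fully excluded, and the original table must be checked first. But the faults seen are displaced or surplus marks, not dropped ones, and the neighbouring rows keep Visit 27 in place.

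The second objection is that an exit test is a preference. The documents do not require one, and the use that Section 8.3.10.3 makes of a positive result is to withdraw the woman, who at exit has already stopped. Contraception is required, a pregnancy learned of later is still reported with no cut-off at exit, follow-up contacts continue, and unscheduled tests are allowed. All of this is true. It makes the number of missed pregnancies small, but it leaves the end of exposure without any scheduled check.

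The third objection is that a urine test close to the last dose can miss a very recent conception, and that the change leaves the on-drug interval from Week 36 to Week 52 at 16 weeks. Both points stand. The test narrows the gap and does not close it. The 88- and 116-day figures are worst cases.

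**Conclusion.** The concern holds for the table as it reads in the text version. Followed as written, the plan gives women who stop early, or who complete without entering A308, no scheduled pregnancy test at or after the end of exposure. Their last scheduled test may be up to 12 weeks old at exit before Week 36, and up to 16 weeks old by Week 52.

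This rests on two assumptions: that the empty Visit 27/ET cell is also empty in the original table, and that the third mark belongs to Visit 13. Confidence is medium for the first reason. The documents do not give the number of women, of exits without rollover or of pregnancies, so the number affected cannot be estimated; the contraception requirement suggests that it is small. This is a gap in safety ascertainment that should be corrected. It does not bear on sample size, error rates or any planned analysis.

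**What to change.** Check the Visit 27/ET cell against the original Table 3. If it is blank, mark pregnancy testing there; the ET visit inherits the mark. In either case, reword footnote d to name the visits as footnote e does: 1, 7, 13, 19 and 27/ET. The footnote edit is worthwhile even if the mark proves to be present, because it removes the ambiguity.

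The cost is one mark, one footnote and one test strip per woman, at a visit that already collects urine for the drug screen and urinalysis. No visit or blood draw is added. The downside is an occasional false positive that needs confirmation.

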8.4.4. Pain Management

Because ALKS 3831 contains samidorphan, a μ -opioid antagonist, patients may experience reduced or ineffective analgesia when taking an opioid analgesic agent concurrently with ALKS 3831, including several days after last dosing of ALKS 3831.

In the event of an emergency, pain management of the subject should include the following:

- Regional analgesia or use of non-opioid analgesics
- If opiate anesthesia or analgesia is required, the subject should be continuously monitored, in an anesthesia care setting, by persons not involved in the conduct of the surgical or diagnostic procedure. The opioid therapy must be provided by individuals specifically trained in the use of anesthetic drugs and the management of the respiratory effects of potent opioids, specifically the establishment and the maintenance of a patent airway and assisted ventilation.
- Close monitoring by appropriately trained personnel in a setting equipped and staffed for cardiopulmonary resuscitation

For subjects requiring emergency opioid analgesics prior to dosing, the study drug should not be administered. If opioid analgesics are required after the study drug has been dosed, it may take several days for opiate sensitivity to be restored, since samidorphan functions as a μ -opioid antagonist and could interfere with opioid-mediated pain management.

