9. TREATMENT OF SUBJECTS

9.1. Study Drug Dose and Administration

Study drugs include

- ALKS 3831 10/10 (10 mg olanzapine/10 mg samidorphan)
- ALKS 3831 15/10 (15 mg olanzapine/10 mg samidorphan)
- ALKS 3831 20/10 (20 mg olanzapine/10 mg samidorphan)

ALKS 3831 will be supplied as a coated bilayer tablet for oral administration.

At Visit 1 and all subsequent visits until EOT, subjects will be given blister cards containing study drug to take at home. Subjects will be instructed to take one tablet by mouth each day, preferably at bedtime. Dosing may be switched to another time at the investigator's discretion if there are tolerability problems; however, frequent switching is discouraged.

Subjects will be instructed to keep all unused tablets in their blister card and to return unused tablets to the study site at their next visit. If dosing is to occur at that visit, the dose should be taken from the subject's next blister card, not from the card they are returning.

If a dose is missed or forgotten, subjects will be instructed to resume regular dosing the following night. Subjects will be instructed not to take a double dose to try to "make up" for the missed dose.

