10.2. Packaging and Labeling

ALKS 3831 will be supplied in blister cards. Blister cards will be in biweekly configurations. Biweekly blister cards will contain 16 tablets, enough for 2 weeks of dosing plus sufficient overage for 2 additional once daily doses.

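### The emergency treatment card is collected at Visit 27 (EOT), usually about half a day after a completer's last dose, while opioid blockade may last several days more (minor safety point)

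*Protocol*

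**What the plan says.** Protocol Section 8.3.12 describes the card. It identifies the subject as taking an opioid antagonist and olanzapine, and it carries a suggested pain management plan and information on opiate blockade. Subjects are to carry it at all times. That section leaves distribution and collection to Table 3, so the working rule is footnote m in Section 8.2: "Emergency treatment card to be dispensed at Visit 1, confirmed at subsequent timepoints, and collected at Visit 27, EOT".

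Section 8.4.4 says that the effect on opioid analgesia outlasts dosing, "including several days after last dosing of ALKS 3831". It adds that after a dose "it may take several days for opiate sensitivity to be restored". Neither sentence gives a number of days. The same section asks for continuous monitoring by specially trained staff if opioids have to be used.

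Section 8.1 sends completers who do not continue into ALK3831-A308 to a 4-week safety follow-up. I found no text that lets a subject who stops study drug keep the card or receive a replacement.

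**The concern.** The card tells emergency staff, who know nothing of the trial, that opioids may not work as expected and need special precautions. Section 8.4.4 says that this need continues after the last tablet. Footnote m takes the card away at the visit that closes treatment. A subject who has an accident or emergency surgery in the next few days could still respond poorly to opioids and would no longer be carrying the warning.

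Only the safety of individual subjects in a short window is at stake. Nothing in the SAP depends on the card.

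**Working it through.** The documents give neither a last-dose date for completers nor a duration of blockade, so there is no figure of the plan's own to reproduce. The check has three steps.

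**1. Last dose to Visit 27 (inferred)**

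Inputs:
- Supply (Section 9.1): "At Visit 1 and all subsequent visits until EOT, subjects will be given blister cards containing study drug to take at home". Subjects are told "to return unused tablets to the study site at their next visit", so leftovers from older cards should not extend the supply.
- Card size (Section 10.2): "Biweekly blister cards will contain 16 tablets, enough for 2 weeks of dosing plus sufficient overage for 2 additional once daily doses".
- Dosing time (Section 9.1): preferably bedtime, but "Dosing may be switched to another time" at the investigator's discretion.
- Window (Table 3, footnote a): ±2 days, which "is allowed throughout the treatment period and during the follow-up period".
- Time of visit: footnote h puts laboratory draws in the morning. I assume that this applies at Visit 27.

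Usual case: with bedtime at 20:00 to 24:00 and a visit at 08:00 to 12:00 (assumed), the interval is (24 − bedtime + visit hour)/24. This runs from (24 − 24 + 8)/24 = 0.33 day to (24 − 20 + 12)/24 = 0.67 day, or about 0.5 day.

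Visits 26 and 27 are 14 days apart, each ±2, so 10 to 18 days. A 16-tablet card covers up to 16 days. Hence d = base + max(0, interval − 16), where base is 0.5 day for bedtime dosing and 1 day for morning dosing with no dose on the visit day.

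| Visit 26 to Visit 27 | d, bedtime | d, morning |
|---|---|---|
| 10 to 16 days | 0.5 | 1 |
| 17 days | 1.5 | 2 |
| 18 days | 2.5 | 3 |

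These are scenarios, not bounds. If the two spare tablets go unused, an 18-day interval gives 0.5 + (18 − 14) = 4.5 days. Missed visits or poor adherence also lengthen d and so shorten the gap. A dose on the morning of Visit 27 would shorten d.

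**2. Time without the card**

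Gap = max(0, B − d), where B is the assumed duration of blockade, taken as 2 to 7 days.

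| B (days) | Gap at d = 0.5 | Gap over d = 0.5 to 3 |
|---|---|---|
| 2 | 1.5 | 0 to 1.5 |
| 3 | 2.5 | 0 to 2.5 |
| 5 | 4.5 | 2 to 4.5 |
| 7 | 6.5 | 4 to 6.5 |

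A zero gap needs d of at least B. For B = 2 that means a 17-day interval with morning dosing, or an 18-day interval. For B = 3 it means an 18-day interval with morning dosing.

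**3. Would Visit 28 be late enough?**

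Visit 28 is 14 days after Visit 27, each ±2, so 10 to 18 days. The earliest case is 0.5 + 10 = 10.5 days after the last dose. The latest is 1 + 18 = 19 days, because the longer values of d need a late Visit 27, which shortens the next interval. Holding the card until Visit 28 therefore covers every B considered. The card would then be out of date for between 10.5 − 7 = 3.5 days and 19 − 2 = 17 days.

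**The case against.** Most of the case against this point concerns its size and the remedy, and much of that stands.

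- **Size.** The duration of blockade is not quantified and the last-dose interval is inferred. The SAP's Follow-up Safety Population (Section 3.2.2) uses more than 7 days after the last dose, by reference to five half-lives. A reader might infer that blockade lasts 7 days. The documents do not say so: that is a product washout rule for follow-up adverse events, and it makes 7 days no more than a plausible upper value.
- **Other sources of information.** A reader might infer that the card is the subject's only warning. Section 17.3 gives each subject a copy of the signed consent form, whose content is not available to me. Section 8.4.2 also says that opioid agonists should be avoided during the study period. I found nothing that asks subjects to carry the consent form, and the advice in Section 8.4.2 does not reach emergency staff.
- **Who is affected.** Footnote m names only Visit 27, EOT. Extending it to early terminators rests on the shared 27/ET column and on Section 7.3, which models the ET visit on Visit 27. Subjects who never return keep their card. Those entering A308 stay on drug, and whether A308 issues a card is not stated here. I place no weight on the X marks in Table 3, which may not have been read correctly.
- **The remedy has its own risk.** The card says that the subject is receiving an antagonist. Kept until Visit 28 it will be out of date for a while, often for longer than the gap it closes: at B = 5, 5.5 to 14 days against a gap of 2 to 4.5. An outdated card could steer staff away from opioids that would work. This is the strongest objection, and it is why the card needs an expiry date.

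**Conclusion.** The point holds as a minor patient-safety improvement of the lowest severity. As written, footnote m removes the card during a period in which Section 8.4.4 says its warning may still apply. This affects completers who do not enter A308 and, by inference, early terminators who attend an ET visit.

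In the usual case of half a day from last dose to visit, the time without the card is 1.5 to 6.5 days for an assumed blockade of 2 to 7 days. With a blockade of 2 to 3 days and a longer interval since the last tablet, it can be zero. The number of subjects concerned is not given.

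A reader might infer a material safety failure or a countable excess of harm. The documents do not support that: they give neither a rate of opioid-requiring emergencies nor a duration of blockade. No endpoint, analysis population or estimate changes.

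**What to change.** Replace footnote m with text to this effect:

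> Issued at Visit 1; possession checked at later visits. At Visit 27/ET, site staff write on the card the date of the last dose, a statement that opioid blockade may persist for several days after it, and the date after which the card no longer applies. Subjects stopping ALKS 3831 keep the card and return it at Visit 28, or discard it after the written date if they do not attend. Subjects entering ALK3831-A308 keep the card until they receive the A308 card.

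The A308 sentence matters because those subjects remain on drug and should not lose the card before a replacement is assured.

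**Cost.** One footnote in a protocol amendment and a short handwritten entry on each card. The sponsor must choose the number of days behind the expiry date, which the documents do not supply. No new visit is needed for completers, who already have Visit 28. Early terminators attend follow-up only if willing, so some cards will not come back. Some will be carried for days to about two weeks after blockade has ended (3.5 to 17 days in the scenarios above). The written dates limit that risk but do not remove it.
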